8.3 Investigator Selection Criteria

The data for this NIS will be collected from rheumatology outpatient departments and office-based rheumatologists in Germany routinely treating patients with RA. Physicians from about 200 sites which are spread across all of Germany will participate in this NIS.

Principal Investigator:

[REDACTED]

[REDACTED]

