## 1.10 Biometrics concept of AGIL-CV

*Biometrics concept as an addition to AGIL-CV:*

Using stepwise regression analyses with forward and backward techniques, all partial correlations between the primary parameters and the other disease and patient characteristics are determined at baseline. The impact of disease and patient characteristics on the changes in each of the primary parameters is established by means of these regression analyses at Months 12, 24 and 60. In particular, the DAS28 response (defined as the critical difference [dcrit] of  $\leq -1.8$  points, constituting an improvement of 1.8 points in DAS28) or DAS28 nonresponse was used as a coded variable.

In addition, the observed difference between the DAS28 responders (patients with a dcrit of  $\leq -1.8$  at 5 of 7 visits) and the DAS28 nonresponders (dcrit  $> -1.8$ ) is tested using the general linear model. Missing data are replaced using the Last observation carried forward (LOCF) method.

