8.2 Number of Patients to be Enrolled

The NIS will include about 2500 patients in order to provide for the final evaluation of missed working days a sample size of $n = 850$ employed patients who are temporarily on sick leave during the study (see also Section 12.1 “Sample Size Calculation”).

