12.1 Sample Size Calculation

The primary parameter of this documentation is work productivity, which is captured by the number of missed working days. The sample size calculation is based on the results of an interim analysis of a documentation of adalimumab in RA with 4640 patients, of whom 1417 patients had been employed part time or full time. The mean number of missed working days was 26 days (standard deviation of 55 days) during the last 12 month prior to adalimumab therapy. The correlation between baseline and follow-up report is estimated with $r = 0.5$. According to these numbers, 850 employed patients are required to detect a mean difference of 5 days within 12 months at the 0.05 significance level (two-sided) with a power of 0.80. Since 30 % of patients are employed, a total number of about 2500 employed and non-employed patients are required in order to detect the specified difference in missed working days.

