12.5 Biometric Concept

The general biometric approach consists of the realization of the analyses described in section 7 “Study Objectives”. The analysis principally uses descriptive statistical methods, supported by regression statistical methods and subgroup analysis.

By forward and backward stepwise regression, those patient and disease characteristics (baseline values of all target parameters, disease duration, previous therapies, demographic and anthropometric data, health-related quality of life etc.) will be selected which show a statistically significant partial correlation with the parameters of therapeutic success at month 3 (improvements in the number of affected joints [DAS28], HAQ, number of missed working days, and WPAI). Due to the clear temporal relation between the baseline values and the treatment effects at month 3, the selected predictors can be interpreted both as causal explanation and as prognosing factors concerning therapy-modifying influencing variables (since an reactive influence of the 3-month values on the baseline values can be ruled out). Additionally, the strength of the relationship between the predictors and the parameters of therapeutic success will be determined.

The impact of the features determined by regression analysis on the therapeutic success will be illustrated by subgroup analysis. Subgrouping will be done according to content-related considerations: Regarding disease activity, patients will be classified into groups with high or low DAS28 values (lower and higher 5.1 units, respectively). Regarding age, patients will be classified into groups with high or low age (lower and higher 40 years, respectively).

The impact of adalimumab therapy on health-related quality of life (EQ-5D), the number of physician visits and hospitalizations, the days of impairment in non-occupational activities, and the subjective symptoms (morning stiffness, pain, exhaustion/fatigue) will be descriptively evaluated and additionally analyzed by between-group comparison.

The tolerability analysis will be based on MedDRA coded AEs and SAEs. Incidence rates will be reported on the “Preferred Term” and “System Organ Class” levels for all patients as well as for subgroups of patients with different degrees of disease activity as well as with different previous and concomitant therapies and diseases.

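### About 2500 patients come from about 200 sites, but no stated model or sample size allows for site, so some tests are too liberal and site differences can pass as effects of patient characteristics

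*Combined protocol and SAP*

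**What the plan says.** **Structure.** AGIL section 8.2: "The NIS will include about 2500 patients in order to provide for the final evaluation of missed working days". Section 8.3: "Physicians from about 200 sites which are spread across all of Germany will participate in this NIS". The sites are outpatient departments and office-based practices. Section 8.5.1 leaves indication, choice and conduct of treatment to the physician. Section 8.5.3 builds the DAS28 from data on the physician form, including the joint counts.

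**Models.** AGIL section 12.5 begins its regression plan "By forward and backward stepwise regression, those patient and disease characteristics" and keeps those with a significant partial correlation with outcome at Month 3. It then says that the selected predictors may be read as causal as well as prognostic. AGIL-CV section 1.10 uses stepwise regression as well, and its comparison of DAS28 responders with nonresponders "is tested using the general linear model". AGIL section 12.4 sets a nominal two-sided level of 0.05.

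**Sample size.** AGIL section 12.1 asks for 850 employed patients "with a power of 0.80". AGIL-CV section 1.9 works from blood pressure means and standard deviations. Neither allows for clustering.

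No section of either document mentions a site term, a random effect, a robust standard error, an ICC or a design effect. Section 12 of the AGIL plan leaves the details to a separate SAP, to be finalised before the first interim analysis.

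**The concern.** Patients at one site share prescribing habits, co-medication policy and, for joint counts, the people who count. Two things follow if outcomes correlate within site.

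- **Precision.** Ordinary standard errors of a mean change, or of a predictor that clusters by site, are too small, and tests at 0.05 reject too often.
- **Confounding.** A characteristic that differs between practices can be selected because of who treated and assessed the patient. The AGIL synopsis singles out previous biologic therapy as a predictor of interest for the clinical outcomes, and this plausibly varies by practice. Section 12.5 rests its causal reading on baseline preceding Month 3. Temporal order does not remove differences between sites.

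The second is the more serious, because the plan selects predictors by significance and then interprets them causally.

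**Working it through.** **1. The plan's own figure.** Inputs from AGIL section 12.1: "The mean number of missed working days was 26 days (standard deviation of 55 days"), correlation 0.5, difference 5 days, two-sided 0.05, power 0.80.

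SD of change = 55 × √(2 × (1 − 0.5)) = 55.

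n = (55 × (1.960 + 0.842) / 5)² = 950.

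The stated 850 is not reproduced; 850 gives 75.5% power. This discrepancy is separate and has nothing to do with clustering. It does confirm that the calculation treats patients as independent.

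**2. Patients per site (m), with 200 sites.**
- All patients: 2500/200 = 12.5
- Employed target: 850/200 = 4.25 (or 30% of 2500 = 750, giving 3.75)
- Interim groups in section 12.6: 800/200 = 4, if all sites contribute

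**3. Means and predictors constant within site.** Design effect D = 1 + (m − 1) × ICC. The SE is too small by the factor √D. True two-sided error = 2 × (1 − Φ(1.96/√D)). The ICC values are assumptions.

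| Patients (m) | ICC | D | √D | Effective N | True error |
|---|---|---|---|---|---|
| 2500 (12.5) | 0.01 | 1.12 | 1.06 | 2242 | 6.3% |
| | 0.05 | 1.58 | 1.25 | 1587 | 11.8% |
| | 0.10 | 2.15 | 1.47 | 1163 | 18.1% |
| 850 (4.25) | 0.01 | 1.03 | 1.02 | 823 | 5.4% |
| | 0.05 | 1.16 | 1.08 | 731 | 6.9% |
| | 0.10 | 1.33 | 1.15 | 642 | 8.9% |
| 800 (4) | 0.01 | 1.03 | 1.01 | 777 | 5.4% |
| | 0.05 | 1.15 | 1.07 | 696 | 6.8% |
| | 0.10 | 1.30 | 1.14 | 615 | 8.6% |

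With 750 employed the errors are 5.3%, 6.6% and 8.3%.

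Unequal site sizes raise D to 1 + ((cv² + 1) × m − 1) × ICC, where cv is the coefficient of variation of site size. With m = 12.5, cv = 1 and ICC 0.05, D = 1 + (25 − 1) × 0.05 = 2.20, and the true error is 18.6%.

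Dropout works the other way. If half remain at Month 60 (the rate quoted in AGIL-CV section 1.9), m = 6.25, D = 1.05, 1.26 and 1.53, and the errors are 5.6%, 8.1% and 11.2%.

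**4. Regression on a predictor with no true effect.** Simulation with 2500 patients, 200 sites and 2000 runs per setting; no site term unless stated.

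| Predictor | Outcome ICC | False positives |
|---|---|---|
| Varies freely within site | 0.05 to 0.10 | 4.7 to 5.5% |
| ICC 0.10, site effects unrelated to outcome | 0.10 | 6.2% |
| ICC 0.30, site effects unrelated | 0.10 | 8.4% |
| Constant within site | 0.05 / 0.10 | 13.4% / 19.0% |
| ICC 0.05, site effects correlated 0.3 with outcome's | 0.05 | 11.7% |
| ICC 0.10, site effects correlated 0.3 | 0.10 | 32.4% |

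In the settings with correlated site effects, adjusting for site brought the rate back to 4.3 to 5.2%. The excess there is bias in the coefficient, so a wider standard error would not cure it.

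**The case against.** - **The SAP may deal with it.** True: independence is inferred from silence. A reader might infer that the plan declares patients independent; it does not. But sections 12.5 and 1.10 already name the models, and the SAP is the natural place for the correction.
- **The analysis is mainly descriptive and exploratory.** Section 12.4 uses that to waive multiplicity adjustment. It still tests at 0.05, and section 12.5 still selects by significance. No section specifies confidence intervals, so the point concerns the tests first and intervals only where they are reported.
- **The large error rates do not fit most planned tests.** This stands. The 12% and 18% apply to mean changes and predictors constant within site, with all 2500 patients. Among 240 employed patients at an interim analysis (30% of 800, 1.2 per site), the error is 5.2% even at ICC 0.10. The 32% also needs an assumed correlation between site effects.
- **Rater differences cancel in change scores.** Partly true: a stable additive bias largely does. Missed days, WPAI, HAQ and EQ-5D are reported by patients, so the reader effect concerns only joint counts and DAS28. Site differences in care can still affect the other outcomes.
- **A reader might equate sites with physicians.** Section 8.3 gives a number of sites, and a site may have several physicians. The correlation that matters here is the one within site.

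**Conclusion.** The point holds in limited form. The stated models and sample sizes make no allowance for about 200 sites.

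The size depends on an ICC that the documents do not give, and on average site sizes. Under assumed ICCs of 0.01 to 0.10, the true error of a nominal 5% test is about 6 to 18% for mean changes and site-level predictors in all 2500 patients. It is about 5 to 9% for missed working days and the interim groups, and close to 5% for predictors that vary freely within site.

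The risk of site confounding is the stronger part, because section 12.5 intends a causal reading. Whether previous biologics or co-medication do cluster by site is plausible but not shown.

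A reader might infer that clustering is stronger in AGIL-CV, because section 1.5 restricts it to selected sites. The documents do not support that: they give no number of sites, and sites with a shared routine could be more alike. Its outcomes are also laboratory values, vital signs and body measurements. Joint counting enters there through the DAS28 responder grouping.

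**What to change.** In AGIL section 12.5, AGIL-CV section 1.10 and the SAP:

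1. Use site-clustered robust standard errors or a random site intercept for tests of mean change, for any intervals reported with them, and for the final regression models. Stepwise selection does not carry over directly to mixed models, so apply this to the model that remains after selection.
2. For each predictor to be read as causal, also report a within-site estimate, from site fixed effects or by splitting the predictor into site mean and within-site deviation. Robust errors leave the coefficient unchanged, and a random intercept removes only part of the confounding.
3. Report the ICC for DAS28 and joint counts.

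**Cost.** Some intervals become wider, and there is a little more analysis work. No new data collection appears necessary: section 11 issues CRF folders by centre and section 10 sends queries to centres, so site should be linkable, although the plan does not say so outright.

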8.4 Study Duration

The duration of the whole NIS is estimated to be about 9 years.

Study start: March 2009

Recruiting phase: March 2009 – March 2012

Data completion: March 2017

Data analysis and final report: March 2017 – March 2018

For each individual patient, the NIS starts with the enrollment in the long term documentation at the beginning of the treatment with adalimumab and ends either after 5 years or with the termination of the adalimumab therapy.

8.5 Study Conduct

8.5.1 Schedule of Observations

This NIS will be a single-arm, multi-center, prospective cohort study.

Non-interventional studies are one of several methodical instruments to collect information on drugs available on the market. Their defining characteristic is the lack of influence on the relationship between individual physicians and patients in respect to determining indication as well as choice and conduct of the treatment, while at the same time allowing for the structured and systematic collection of treatment data (see also Section 6). Adalimumab must not be prescribed for the purpose of including a patient in this NIS.

Patients will be informed about the type of therapy, alternate therapies, and risks, and they have to provide a written informed consent to the data collection on the documentation forms before the start of therapy. The presence of the written informed consent is documented on the base documentation form. Before enrollment in the NIS, the patients will be made anonymous. Abbott will only receive access to anonymous data. Abbott can only identify the patients via their patient number.

The visits are scheduled according to the recommendations of the Deutsche Gesellschaft für Rheumatologie (German Society for Rheumatology): The documentation consists of patient self-assessments as well as assessments by the physician. The following tables provide an overview of the observations to be documented by the physician ([Table 1](#)) and the patient ([Table 2](#)).

Due to long time intervals between the scheduled visits (one year after month 12), interim documentation forms will be provided for non-scheduled visits in order to document clinically significant events.

Table 1. Physician Schedule

	Month							
	0	3	6	12	24	36	48	60 ¹
Demographic data	X							
Inclusion criteria	X							
Indication HUMIRA®	X							
Medical history / change history	X	X	X	X	X	X	X	X
Radiologic findings ²	X			X	X	X	X	X
Previous RA therapies	X							
Concomitant diseases and therapies ³	X	X	X	X	X	X	X	X
Current HUMIRA® therapy ⁴	X	X	X	X	X	X	X	X
RA-related concomitant medication ⁴	X	X	X	X	X	X	X	X
Disease activity ⁵	X	X	X	X	X	X	X	X
Current joint status ⁵	X	X	X	X	X	X	X	X
Morning stiffness	X	X	X	X	X	X	X	X
Rheumatoid nodules	X							
Joint (replacement) surgery	X			X	X	X	X	X
Laboratory values: CRP, ESG, Hb-value, ⁶	X	X	X	X	X	X	X	X
Laboratory values: RF, CCP ⁶	X							
Laboratory values: Hepatitis B, Hepatitis C, tuberculosis screening, TB prophylaxis (if necessary) ⁶	X	X ⁷	X ⁷	X ⁷				
Adverse events		X	X	X	X	X	X	X
Patient's compliance		X	X	X	X	X	X	X

¹ Month 60 or last visit

² after baseline visit (month 0) only if current radiograph is available or if indicated

³ after baseline visit (month 0) only for newly developed diseases or changed therapy

⁴ after baseline visit only for changes in therapy or dose

⁵ Data are part of the DAS28 (Disease Activity Score)

⁶ after baseline visit (month 0) only if data is available or if indicated

⁷ only TB prophylaxis documented

Table 2. Patient Schedule

	Month							
	0	3	6	12	24	36	48	60
Personal data	X							
Education	X							
Professional status	X		X	X	X	X	X	X
Missed working days (last 6 months)	X		X	X	X	X	X	X
Physician visits and hospitalization (last 6 months)	X		X	X	X	X	X	X
Days of impairment in non-occupational activities	X		X		X	X	X	X
Work ability (WPAI)	X	X	X	X	X	X	X	X
Exhaustion/fatigue (last 7 days)	X	X	X	X	X	X	X	X
Pain (last 7 days)	X	X	X	X	X	X	X	X
Functionality (HAQ)	X	X	X	X	X	X	X	X
Health-related quality of life (EQ-5D)	X	X	X	X	X	X	X	X
Patient's assessment of adalimumab ther- apy compared to previous therapies		X	X	X	X	X	X	X
Participation Abbott Care service program	X	X	X	X	X	X	X	X

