Course of work productivity and work ability, the course of health-related quality of life, and changes in functionality under long term treatment with adalimumab will be documented. The numbers of patients included in the NIS allow identifying and quantifying the impact of disease and patient characteristics on the therapeutic success.

7 Study Objectives

In this NIS, a long term documentation of treatment with adalimumab in RA patients over 60 months with 8 data collection points (visits) is planned. The documentation will be performed by the physician as well as by patient's self-assessment.

The primary objective is to explore the therapeutic success by interim analyses after 12 and 24 months of treatment as well as by the final analysis after 60 months of treatment. Improvements concerning the following target variables will be evaluated (with regard to the respective baseline value):

- the number of missed working days
- the self-assessed work ability (WPAI)
- the severity of clinical symptoms (number of tender and swollen joints, CRP and ESR, respectively; total score DAS28)
- Severity of functional impairment (HAQ)
- The health-related quality of life (EQ-5D)

At month 3, patient and disease characteristics will be evaluated with regard to their additional impact on changes in the number of affected joints (DAS28), in the HAQ, and in the WPAI. The impact on the number of missed working days will be evaluated at month 6.

The secondary objective is to document the therapeutic success by interim analyses at month 12 and 24 months as well as by the final analysis after 60 months. The therapeutic success will be evaluated by the following variables:

- The number of physician visits
- The number and duration of hospitalizations
- The number of days of impairment in non-occupational activities
- The duration of morning stiffness, pain, exhaustion/fatigue

- The reduction of number and dose of concomitant medication
- Patient's assessment of adalimumab therapy compared to previous therapies

Target parameters for safety evaluation of adalimumab are:

- The evaluation of safety and tolerability by the documentation and analysis of serious adverse events (SAEs) and adverse events (AEs).
- Evaluation of safety and tolerability for subgroups of patients with common frequent concomitant diseases, especially diabetes type II, cardiovascular, liver, and renal insufficiencies, and related concomitant medications.

8 Investigational Plan

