8.5.2 Description of Activities

The following data will be documented (if assessed in routine care):

Physician:

Baseline Visit (Month 0)

Demographics and History

Demographic Data (age, gender, height, weight)

Inclusion criteria (moderate to severe active RA and/or severe, active, and progressive RA, signed informed consent)

Exclusion criteria according to Fachinformation (hypersensitivity, active tuberculosis, other severe infections [e.g. sepsis, opportunistic infections], moderate to severe heart insufficiency [NYHA class III/IV])

HUMIRA®
AGIL

Indication for the current HUMIRA® therapy

Radiological findings of affected joints

History (including initial diagnosis of RA and tobacco use)

Previous therapies: DMARD (MTX, SASP, leflunomid), glucocorticoids, biologics (infliximab, etanercept, rituximab, tocilizumab, abatacept), date of biologic discontinuation

Concomitant diseases and concomitant medication

Current RA therapy

Current HUMIRA® therapy

Additional DMARD, systemic glucocorticoids, analgetics, NSAID, COX inhibitors

Current status

Disease activity, joint status (28 joints, tender, swollen), morning stiffness, rheumatoid nodules, previous joint surgery

Laboratory values (RF, CCP, CRP, ESR, Hb-value, hepatitis B, hepatitis C, tuberculosis screening, TB prophylaxis, pregnancy test in women with childbearing potential)

Follow-up Visits (Month 3, 6, 12, 24, 36, 48, 60)

Change history

Current therapy (RA therapy and concomitant medication)

Disease activity

Joint status

Morning stiffness

Joint (replacement) surgery (beginning month 12)

Radiographic findings (beginning month 12)

Laboratory values (CRP, ESR, Hb-value, other laboratory values if indicated)

(S)AE

Patient's compliance

Patient:

Baseline Visit (Month 0)

Personal data

Education

Professional status

Missed working days, days of impairment in non-occupational activities

Physician visit, hospitalization

WPAI, HAQ, and EQ-5D

Exhaustion/Fatigue, pain
Participation in the Abbott Care service program

Follow-up Visits (Month 3, 6, 12, 24, 36, 48, 60)

WPAI, HAQ, and EQ-5D
Exhaustion/Fatigue, pain
Patient's assessment of adalimumab therapy
Participation in the Abbott Care service program

Follow-up Visits (Month 6, 12, 24, 36, 48, 60)

As above, additionally:
Missed working days, days of impairment in non-occupational activities
Physician visits, hospitalization
Changes in the professional status

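### Table 2 leaves out impairment days at Month 12, and Section 12.1 states power for a change in a 12-month count of missed working days that 6-month recall cannot provide

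*Combined protocol and SAP*

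**What the plan says.** All references are to the combined protocol and SAP.

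**Impairment days.** In Table 2 (Section 8.5.1) the row "Days of impairment in non-occupational activities" carries a mark at Months 0, 6, 24, 36, 48 and 60. Months 3 and 12 are blank. Section 8.5.2, under "Follow-up Visits (Month 6, 12, 24, 36, 48, 60"), lists "Missed working days, days of impairment in non-occupational activities". Section 7 sets the secondary objective as to "document the therapeutic success by interim analyses at month 12 and 24 months", with a final analysis at 60 months, and names "The number of days of impairment in non-occupational activities" among its variables.

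**Missed working days.** Section 12.1 names this as the primary parameter. Its planning figures are a mean of 26 and an SD of 55 days over the 12 months before adalimumab, a baseline/follow-up correlation of 0.5, and a difference of 5 days within 12 months. From these it derives 850 employed patients for power 0.80 at two-sided 0.05. Section 8.2 ties the 850 to the final evaluation. Table 2 collects "Missed working days (last 6 months") at Months 0, 6, 12, 24, 36, 48 and 60. For the primary objective, Section 7 states: "Improvements concerning the following target variables will be evaluated (with regard to the respective baseline value"). Section 8.5.1 acknowledges the spacing of visits: "Due to long time intervals between the scheduled visits (one year after month 12").

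**The concern.** Two places where the data collected and the analysis planned do not match.

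(a) One schedule omits an item at a visit where another section requires it and where an interim analysis depends on it. If the Month 12 form was built from Table 2, that analysis has no data, and no later SAP can recover a question that was not asked.

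(b) The sample-size statement for the named primary parameter is in a different unit from the data. If the change that 12.1 describes cannot be computed, its power does not apply to the change that will be analysed, and a reader cannot tell what difference 850 patients can detect.

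**Working it through.** **Part (a): the passages side by side**

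| Source | Impairment days at Month 12 |
|---|---|
| Table 2 | blank |
| Section 8.5.2 | listed |
| Section 7 | secondary variable, analysed at Month 12 |

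The neighbouring rows for professional status, missed working days and physician visits are all marked at Month 12, so the blank is specific to this row.

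**Part (b), step 1: which 12-month counts can be built from 6-month reports**

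- Baseline: the Month 0 report covers only the 6 months before treatment. A 12-month baseline is not available.
- First year: the Month 6 and Month 12 reports add up to a full 12-month follow-up count.
- Month 24: the report covers months 19–24; months 13–18 fall outside every scheduled report.
- Month 60: the report covers months 55–60; months 49–54 are likewise missing.

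So the 12-month change from baseline cannot be formed at any analysis time. At Month 60 neither side of it exists. The interim forms in Section 8.5.1 are for clinically significant events at unscheduled visits and do not fill these gaps.

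**Step 2: the plan's own figure, from 12.1 inputs only**

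Paired comparison, two-sided 0.05:

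- SD of change = 55 × √(2 × (1 − 0.5)) = 55 days.
- n for 80% power = ((1.960 + 0.842) × 55 / 5)² ≈ 950 by the normal approximation; 952 by the paired t-test.
- Power at 850: (5/55) × √850 = 2.65, and 2.65 − 1.96 = 0.69, giving about 0.755; by the paired t-test, 0.754.
- Difference detectable at 850 with 80% power = 5.29 days.

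The stated 850 is not reproduced. It would need a correlation of about 0.55 instead of 0.5.

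**Step 3: illustrations on the 6-month scale**

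The documents give no 6-month SD or correlation, so the following are assumptions: equal SD in each half-year, and half-year correlations a, b, c at lags 1, 2, 3 chosen so that the 12-month correlation (a + 2b + c)/(2 + 2a) stays at 0.5. The effect is halved to 2.5 days per 6 months.

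- SD6 = 55/√(2 + 2a)
- SD of change, Month 6 alone = SD6 × √(2(1 − a))
- SD of change, Month 12 alone = SD6 × √(2(1 − b))
- SD of change, average of both = SD6 × √(1 + (1 + a)/2 − (a + b))

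Results at 850 patients are given as Month 6 / Month 12 / average:

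| a, b, c | SD6 | SD of change | Power for 2.5 days | Detectable at 80% (days per 6 months) |
|---|---|---|---|---|
| 1/3, 1/3, 1/3 | 33.7 | 38.9 / 38.9 / 33.7 | 0.465 / 0.465 / 0.580 | 3.74 / 3.74 / 3.24 |
| 0.5, 0.375, 0.25 | 31.8 | 31.8 / 35.5 / 29.7 | 0.630 / 0.536 / 0.688 | 3.05 / 3.42 / 2.86 |
| 0.7, 0.425, 0.15 | 29.8 | 23.1 / 32.0 / 25.4 | 0.883 / 0.624 / 0.818 | 2.22 / 3.08 / 2.44 |

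If the 5 days is meant per 6 months, the lowest power among these cases is 0.963. The cases are examples, not limits, and cover the first year only; nothing in the documents gives a correlation for Month 24 or Month 60.

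**The case against.** On (a), Table 2 is introduced only as an overview, and Section 11 puts all data specified in Section 8.5 on the case report form. Section 8.5.2 belongs to 8.5 and lists the item, so the form may well carry it. This makes the harm conditional but does not settle the conflict, because Table 2 is also part of Section 8.5.

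On (b), the objective is change from baseline, and the same 6-month report is collected at Month 0 and at every analysis time, so a like-for-like analysis exists throughout. That is correct: this is not a loss of the primary parameter. It can also be said that the 12-month limit in 12.1 means the time of assessment. Even so, the SD of 55 belongs to a 12-month count and does not fit a 6-month one.

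Finally, the analyses are exploratory and mainly descriptive (Sections 12.4 and 12.5), no decision rule depends on 0.80, and the illustrative powers rest on correlations not in the documents. The shortfall within 12.1 is a separate matter from recall and is modest: 5.29 days against 5. These points limit the seriousness. They do not make the power statement correct.

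**Conclusion.** Both parts hold, and both should be corrected.

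(a) Table 2 contradicts Sections 8.5.2 and 7 in one cell. If the form follows the table, a secondary variable is missing for every patient at the Month 12 interim analysis (about 800 planned, Section 12.6). The form is not among the documents, so this remains conditional.

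(b) The 0.80 in 12.1 refers to a change in a 12-month count that the schedule cannot supply. The direction and size of the effect of the shorter window on power are not determined by the documents: the illustrations for a 2.5-day effect run from about 47% to 88%, and a 5-day effect per 6 months gives at least 96% in every case tried. The study is therefore not shown to be underpowered for the 6-month change; its power for that change is unstated. Apart from the recall window, and with no added assumption beyond a paired t-test, the 12.1 inputs give 75% power at 850, with 952 needed for 80%.

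**What to change.** (a) Mark Month 12 for impairment days in Table 2 and confirm that the Month 12 patient form contains the item. Cost: one table cell and one form check.

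(b) Define the endpoint as missed working days in the 6 months before each visit, compared with the 6-month baseline report. State whether the first-year analysis uses Month 12 alone or the average of Months 6 and 12, and that Months 24 and 60 use the single 6-month report. Restate the detectable difference and power in 12.1 in that unit, using a 6-month SD and baseline/follow-up correlation if they can be obtained and a stated range if not, and correct the arithmetic at the same time. Cost: rewording 12.1 and finding, or bracketing, two planning values. The restated power may come out above or below 0.80. No visit or questionnaire is added.
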